9.7.1.2.1 Suspected Drug-Induced Liver Injury

As outlined in the protocol for Study A4250-008, patients with laboratory criteria that meet any of the following are considered suspected events of DILI and undergo review and adjudication of the event aetiology by the DSMB:

- ALT or AST $\geq 5 \times$ ULN if ALT or AST was normal at Baseline, or an absolute threshold of 800 U/L, whichever comes first
- ALT or AST $\geq 3 \times$ Baseline if ALT or AST was abnormal at Baseline, or an absolute threshold of 800 U/L, whichever comes first
- ALT or AST $\geq 3 \times$ Baseline or an absolute threshold increases of +300 U/L, whichever comes first, and total bilirubin $> 2 \times$ ULN if total bilirubin was normal at Baseline
- ALT or AST $> 5 \times$ ULN if they are normal at Baseline, or absolute threshold increases of +300 U/L if ALT or AST $>$ ULN at Baseline in presence of normal LDH and CPK
- Doubling of total bilirubin if total bilirubin was < 3 mg/dL at Baseline and total bilirubin is greater than $2 \times$ ULN unrelated to hemolysis or established genetic diseases, such as Gilbert's Syndrome.
- Increase in total bilirubin by > 3 mg/dL if total bilirubin was ≥ 3 mg/dL at Baseline
- INR increase to > 1.5 if INR was normal at Baseline and increase is refractory to Vitamin K administration
- INR increase by > 0.4 if INR was abnormal at Baseline and increase is refractory to Vitamin K administration

- Any increase in total bilirubin and transaminases if accompanied by either a symptom of clinical hepatitis (vomiting, nausea, right upper quadrant pain) or immunological reaction (rash or 5% eosinophilia)

9.7.1.2.2 Liver Decompensation Adverse Events

Events either identified by Investigators or meeting the Albireo definition of liver decompensation will undergo review and adjudication by the DSMB. Patients who meet either of the following criteria undergo review and adjudication of the event aetiology by the DSMB for liver decompensation:

- INR elevation >1.5 that is refractory to vitamin K administration
- In a patient with portal hypertension and cirrhosis, transition to decompensated cirrhosis evidenced by any of the following:
 - Presence of ascites
 - Hepatorenal syndrome
 - Portopulmonary hypertension
 - Hepatopulmonary syndrome
 - Variceal haemorrhage
 - Hepatic encephalopathy

9.7.1.2.3 SMQ Drug-Related Hepatic Disorder AEs:

Events in the Standardised MedDRA query SMQ *Drug Related Hepatic Disorders; Severe Events Only* (SMQ No. 20000007) that are not captured in any of the above parameters will be presented to the DSMB for review.

The data of all adjudicated hepatic events provided by the DSMB will also be listed.

9.7.2 Clinical Laboratory Evaluations

Clinical laboratory test results will be listed.

The following laboratory variables will be analyzed.

- Hematology:
 - Red blood cells and platelets: hemoglobin, hematocrit, red blood cell count, and platelet count
 - White blood cells: white blood cell count, neutrophils, lymphocytes, monocytes, basophils, and eosinophils
- Clinical chemistry:
 - Metabolism: total cholesterol, triglycerides, creatine kinase, albumin
 - Electrolytes: sodium, potassium, chloride, calcium
 - Renal function: creatinine, blood urea nitrogen, estimated glomerular filtration rate
 - Liver function: ALT, AST, Alkaline phosphatase (and isoenzymes as applicable), direct bilirubin, total bilirubin, gamma-glutamyl transferase
 - Pregnancy test: Serum β -human chorionic gonadotropin (all female patients with positive urine pregnancy test)
- Urinalysis:
 - Urinalysis for quantitative analysis: pH, proteins, glucose, blood, ketones, leukocytes, and nitrites
- Other Labs: Vitamin A and E, 25-hydroxy vitamin D, INR, Alfa-fetoprotein (AFP), and Prothrombin Time

❖ Quantitative Analyses

For all laboratory variables above, descriptive statistics for clinical laboratory values (in SI units for all tests, and in conventional units for selected tests ([Appendix F](#)) and absolute changes from baseline at each post-baseline visit ([Appendix B](#)) will be presented. The change to the last visit will also be summarized. Central laboratory data will be used for the summary. If central laboratory data are not available due to COVID-19 or other reasons, local laboratory data will be used, if available.

Change from baseline in ALT, AST, GGT, direct bilirubin, total bilirubin will be summarized by visit using descriptive statistics. Figure of mean (\pm standard error [SE])

changes from baseline 2 will be provided at each available post-baseline visit. The figures will only present results in a treatment group if there's data for at least 5 patients at that visit; if all treatment groups at that visit do not have at least 5 patients' data, that visit will not be presented in the figure.

Evaluation of drug-induced serious hepatotoxicity (eDISH) plots will be presented for baseline and post-baseline liver function (ALT vs total bilirubin). Baseline eDISH plot will present concurrent levels of baseline ALT vs. total bilirubin as multiples of upper limit of normal (ULN). Post-baseline eDISH plot will present concurrent levels of peak ALT on treatment vs. peak total bilirubin within 30 days of peak ALT as multiples of ULN. In addition, a modified eDISH plot will present concurrent peak ALT vs peak total bilirubin as multiples of individual patient baseline values. Corresponding summary tables will be provided.

❖ Analyses according to reference normal range

Shift tables from baseline to the highest and lowest post-baseline value for quantitative variables will be presented for the clinical laboratory parameters. The laboratory results will be classified as low, normal, and high based on the normal range that was provided by central/local laboratories.

For ALT, AST and total bilirubin, a shift table based on the following classifications (per DILI guidance and CTCAE) will be presented:

- ALT and AST: ≤ 3 ULN, > 3 and ≤ 5 ULN, > 5 and ≤ 10 ULN, > 10 ULN
Total Bilirubin: ≤ 2 ULN and > 2 ULN

❖ Liver Monitoring

Furthermore, a listing of patients meeting the following criteria for liver monitoring will be provided as follows:

- (ALT or AST $\geq 3 \times$ baseline or absolute threshold increase ≥ 300 U/L) and total bilirubin > 2 ULN (normal baseline) at the same visit
- ALT or AST > 5 ULN (normal baseline) or increase ≥ 300 U/L (baseline ALT or AST $>$ ULN) in presence of normal LDH and CPK at the same visit

- INR increased to >1.5 (normal baseline) or increased by >0.4 relative to baseline (abnormal baseline)
- Total bilirubin $\geq 2 \times$ baseline (baseline total bilirubin <3 mg/dL) and total bilirubin is greater than $2 \times$ ULN, or increased by ≥ 3 mg/dL relative to baseline (baseline total bilirubin ≥ 3 mg/dL)

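### The shift table in SAP 9.7.2 has a single bilirubin cut at 2 x ULN, so a patient who starts above it cannot show worsening in that table or in the low/normal/high table

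*SAP*

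**What the plan says.** SAP 9.7.2 plans two shift tables that include total bilirubin.

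- **Reference-range table.** This runs from baseline to the highest and lowest post-baseline values: "The laboratory results will be classified as low, normal, and high based on the normal range".
- **ULN-class table.** "For ALT, AST and total bilirubin, a shift table based on the following classifications (per DILI guidance and CTCAE) will be presented". ALT and AST have four classes, with cuts at 3, 5 and 10 x ULN. Bilirubin has one cut: "Total Bilirubin: ≤ 2 ULN and > 2 ULN".

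The same section has three other displays that bear on bilirubin.

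- **Standard post-baseline eDISH plot.** It uses "peak total bilirubin within 30 days of peak ALT as multiples of ULN".
- **Modified eDISH plot.** "a modified eDISH plot will present concurrent peak ALT vs peak total bilirubin as multiples of individual patient baseline values". Summary tables are to accompany the eDISH plots.
- **Liver-monitoring listing.** "a listing of patients meeting the following criteria for liver monitoring will be provided". Its bilirubin criterion has two branches. With a baseline below 3 mg/dL, bilirubin must at least double and also exceed 2 x ULN. With a baseline of 3 mg/dL or more, it must rise by at least 3 mg/dL.

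SAP 9.7.1.2.1 uses nearly the same two branches as stand-alone criteria for suspected DILI, with DSMB adjudication. SAP 9.7.1 counts suspected DILI in the TEAE overview and in a further table.

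**The concern.** The top bilirubin class is open-ended and begins at 2 x ULN. This is a cholestatic population, and the SAP's own criteria provide for baselines of 3 mg/dL or more. Patients with those baselines would usually sit in the top class before the first dose. Any later rise leaves them where they began, and the table reports no change. The low/normal/high table does not help, because these patients are already high.

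ALT and AST are graded well beyond the lowest abnormal class, so the table can show a transaminase going from moderately to severely raised. It cannot do that for bilirubin. A reader of the study report who turned to the categorical liver tables could take a lack of shifts in this subgroup for a lack of worsening.

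**Working it through.** The plan states no figure to reproduce. The check applies its written rules to example patients.

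**Inputs**
- Shift class (SAP 9.7.2): top class if bilirubin > 2 x ULN, otherwise lower class. The sentence introducing this table does not name the post-baseline value. I take the peak, and the ceiling holds for any choice.
- Listing rule (SAP 9.7.2), with baseline b and peak p in mg/dL: listed if (b < 3 and p ≥ 2b and p > 2 x ULN) or (b ≥ 3 and p − b ≥ 3).
- The SAP does not give the ULN. Assumed 1.0, 1.2 and 1.5 mg/dL, so the cut is 2 x 1.0 = 2.0, 2 x 1.2 = 2.4 and 2 x 1.5 = 3.0 mg/dL.
- The baseline and peak pairs are illustrative and are not trial data.

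**Step 1: who starts at the ceiling.** A baseline of 3 mg/dL or more lies above the cut whenever 2 x ULN < 3, that is, for any ULN below 1.5 mg/dL.

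**Step 2: what the two outputs show**

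| b → p | p/b | p − b | Shift, ULN 1.0 and 1.2 | Shift, ULN 1.5 | Listed |
|---|---|---|---|---|---|
| 0.8 → 3.2 | 4.00 | 2.4 | yes | yes | yes |
| 2.8 → 5.0 | 1.79 | 2.2 | none | yes | no |
| 2.9 → 6.0 | 2.07 | 3.1 | none | yes | yes |
| 3.5 → 6.0 | 1.71 | 2.5 | none | none | no |
| 3.5 → 6.5 | 1.86 | 3.0 | none | none | yes |
| 4 → 9 | 2.25 | 5.0 | none | none | yes |
| 8 → 10.5 | 1.31 | 2.5 | none | none | no |
| 8 → 16 | 2.00 | 8.0 | none | none | yes |

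Every pair that starts above the cut shows no shift, whatever the rise. The listing picks up the larger rises. The pairs 3.5 → 6.0 and 8 → 10.5 appear in neither output at all three ULNs, and 2.8 → 5.0 appears in neither at ULN 1.0 and 1.2.

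**Step 3: would a finer split help?** Take classes >2 to 5, >5 to 10 and >10 x ULN.
- 4 → 9 becomes 4.0 → 9.0 (ULN 1.0), 3.3 → 7.5 (ULN 1.2) or 2.7 → 6.0 (ULN 1.5) x ULN. Each crosses 5.
- 8 → 16 becomes 8.0 → 16.0, 6.7 → 13.3 or 5.3 → 10.7 x ULN. Each crosses 10.
- 8 → 10.5 becomes 8.0 → 10.5, 6.7 → 8.75 or 5.3 → 7.0 x ULN. It crosses 10 only at ULN 1.0.

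The split therefore shows both large rises at every assumed ULN. Smaller rises show only when they happen to cross a cut.

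**The case against.** The strongest reply is that the shift tables are two displays among several, and that the others do show bilirubin worsening in patients with raised baselines. Most of this stands.

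- A bilirubin rise alone, with no link to the ALT peak, is a suspected-DILI criterion in SAP 9.7.1.2.1. Such cases are adjudicated, and suspected DILI is summarised under SAP 9.7.1. But this count is a composite that also takes in ALT, AST, INR and symptom criteria, so it does not say how many patients had worsening bilirubin.
- The listing captures large rises against baseline, as Step 2 shows. It is a listing of patients, though, and no count by group is attached to it.
- By-visit change from baseline is summarised with minimum and maximum (SAP 9.1 and 9.7.2), so an extreme rise at an analysed visit appears as the maximum. It does not give the number of patients who worsened. Where several measurements fall in one window, Appendix B keeps the one closest to the target day, so a peak between visits can drop out.
- The modified eDISH plot scales to each patient's own baseline, which deals directly with raised baselines, and summary tables accompany it.

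A reader might infer that these patients can never show worsening anywhere in the plan, or that all the eDISH displays ignore bilirubin away from the ALT peak. The SAP supports neither reading. The ceiling belongs to the two shift tables. The 30-day window is written only for the standard post-baseline plot. The modified plot calls its values concurrent but states no window.

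It may also be said that the classes follow DILI guidance and CTCAE, as the SAP states. Those sources are not to hand, so this cannot be checked. It would not remove the ceiling in any case.

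**Conclusion.** The point holds as a gap in tabulation. In the ULN-class table and in the low/normal/high table, a patient above 2 x ULN at baseline cannot show bilirubin worsening. The plan specifies no graded, bilirubin-specific table by treatment group that shows peak worsening in such patients. Large rises are not lost, because they reach other outputs. Some moderate rises, such as 3.5 to 6.0 mg/dL, reach neither the shift tables nor the listing.

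The ceiling follows from the stated classes and needs no assumption. The statement that every patient with a baseline of 3 mg/dL or more starts in the top class assumes a ULN below 1.5 mg/dL. The SAP does not give the share of patients above 2 x ULN at baseline, so the effect on the report cannot be sized. The severity is minor: this is a descriptive safety display in an open-label study without formal hypothesis testing, and no efficacy result depends on it.

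**What to change.** Make two changes in SAP 9.7.2.

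1. Split the bilirubin class above 2 x ULN into further multiples of ULN, for example >2 to 5, >5 to 10 and >10. These cuts are a suggestion and do not come from the SAP.
2. Tabulate by treatment group the number of patients who meet the existing bilirubin criterion of the liver-monitoring listing at any post-baseline time. Keep its conditions: at least 2 x baseline and above 2 x ULN if baseline is below 3 mg/dL; a rise of at least 3 mg/dL if baseline is 3 mg/dL or more. If the conditions are dropped, trivial changes would count: 0.3 to 0.6 mg/dL is a doubling, but stays below even the lowest assumed cut of 2.0 mg/dL.

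Both changes use data already collected, and the second uses thresholds already written. The cost is a few extra table rows. The downside is some sparse cells, particularly within treatment groups. The count will still miss rises below the criterion, such as 8 to 10.5 mg/dL. The finer classes will show such rises only when they cross a cut.

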9.7.3 Vital Sign Measurements

Descriptive statistics for vital signs (temperature, systolic blood pressure, diastolic blood pressure, heart rate, respiratory rate, weight, height/length, mid-arm circumference, and BMI) and changes from baseline in vital signs at each post-baseline visit will be presented in a summary table. The change to the last visit will also be summarised. A shift table for the number of patients with changes from baseline to the highest or lowest value ([Appendix E](#)) will be provided by cohort/treatment subgroup during the treatment period.

Vital signs data will be listed.

9.7.4 Physical Examinations

All physical examination data (general appearance, eyes, ears, nose, throat, head/neck/thyroid, lymph nodes, cardiovascular, lungs/chest, abdomen, genitourinary, extremities, skin, musculoskeletal, neurological, and other body systems) will be summarised at each visit with percentages and frequencies along with abnormalities by cohort/treatment subgroup.

Abdominal ultrasound assessments for the liver, including Riedel's lobe, the portal vein, and the spleen also will be summarised descriptively for each visit.

Skin assessments on a 5-point scale (0-4 from no evidence of scratching to cutaneous bleeding, haemorrhage, scabbing) for face, right arm, left arm, right leg, left leg, and torso will be summarised at each visit with percentages and frequencies by cohort/treatment subgroup.

Physical examination and skin assessment data will be listed (including pre-treatment and post-treatment results).

9.8 Other Analyses

9.8.1 Subgroup Analyses

Subgroup analyses will be performed for the primary efficacy endpoints for each of the following subgroups: age groups (<6 months, 6 months to 5 years, 6 to 12 years, and 13 to 18 years, >18 years), each PFIC type (1, 2, other, BRIC), region (US, EU, and RoW), sex, race, ethnicity, baseline serum bile acid (≥ 250 and < 250 $\mu\text{mol/L}$), Child-Pugh classification, Bile Salt Export Pump (BSEP) type of PFIC 2 patients, and the use of UDCA, rifampicin (alone or either one). Subgroup analyses may be conducted for hepatic impairment classification per NCI Organ Dysfunction Working Group (ODWG) if appropriate.

9.8.2 Data Safety Monitoring Board

The DSMB will receive data in the form of tables, figures, and listings (provided by unblinded DSMB statistician from Firma who is independent to the Firma study team). The requirement for blinded or unblinded data is defined in the DSMB charter. Data provided to the DSMB will include, but is not limited to, demographics, baseline characteristics, medical and surgical history, prior and concomitant medications, AE and SAE data (by SOC and PT and by maximum intensity), laboratory data, liver monitoring, vital sign measurements, and abdominal ultrasound and patient disposition data.

10. Changes to Planned Analysis from Study Protocol

The changes to the planned analysis in the protocol are listed below.

1. Endpoints
 - a. Removed below secondary efficacy endpoints
 - i. All-cause mortality
 - ii. Change in use of antipruritic medication at Weeks 24, 48, and 72
 - b. Added below secondary efficacy endpoints
 - i. Change in use of UDCA and/or Rifampicin at Weeks 24, 48, and 72
 - ii. Proportion of responders for pruritus scores

- c. Added below exploratory endpoint
 - i. Change from baseline in episodic flares during the study treatment for BRIC patients.
- d. Added below safety endpoint
 - i. All-cause mortality
- e. Updated secondary and exploratory efficacy endpoints to add the visits during extension period

2. Data Analysis

- a. For the number of patients with events (biliary diversion surgery or liver transplantation or death) and time to event, the comparison to the NAPPED population will be not included in this SAP and will be performed separately.
- b. The following analysis in the protocol “As an exploratory analysis of pruritus and serum bile acids, a comparison of treatment with A4250 120 µg/kg/day during the first 24 weeks of Study A4250-008 versus placebo patients over the 24 week treatment period from Study A4250-005 will be carried out.” was conducted in A4250 ISE analysis because Study A4250-008 did not have post-baseline data of Study A4250-005.
- 3. TEAE definition is updated from “during treatment period” to “during treatment period and within 28 days follow-up after the last dose”.
- 4. Laboratory data will only be considered up to 14 days follow-up after the last dose of Odevixibat for efficacy related endpoints.
- 5. For any hepatic TEAEs, add “Drug related hepatic disorders – comprehensive search SMQ (narrow and broad)”.

11. Appendices

Appendix A: Derived Variables

A list of derived variables for demographic and baseline characteristics, various duration derivations, drug compliance, baseline derivations, and other important derivations applicable for this study is presented in Table 3.

Table 3: Derived Variables for Demographic and Baseline Characteristics, Various Duration Derivations, Drug Compliance, Baseline Derivations, and Other Important Derivations

VARIABLES	FORMULA
Demographic and Baseline Characteristics	
Age at informed consent (in years)	Cohort 1: For patients not from France and Germany, age will be calculated based on date of birth. For patients from France and Germany, only birth year was collected, and July 1 was imputed in the eDC system. The CRF collected age months and age years are based on the imputed date of birth. For analysis purpose, age will be calculated based on collected age months and age years on the Study A4250-005 CRF or the external file (primary source). Cohort 2: For patients not from France and Germany, age will be calculated based on date of birth. For patients from France and Germany, only birth year was collected, and July 1 was imputed in the eDC system. The CRF collected age months and age years are based on the imputed date of birth. For analysis purpose, age will be calculated based on collected age months and age years on the Study A4250-008 CRF or the external file (primary source).
BMI (kg/m ²)	Weight (kg)/[height (m) ²]
PFIC diagnosis (in years)	Will be derived by SAS YRDIF function YRDIF (date of diagnosis of PFIC, date of informed consent, 'ACT/ACT')
Derivation of Duration	
Study day at any visit	Date of interest–date of first dose of study drug. One day is added if this difference is ≥ 0
Extent of exposure (days)	Date of last study drug intake–date of first study drug intake + 1
Drug Compliance	
Compliance based on CRF data	$100 \times [(\text{total number of capsules dispensed} - \text{total number of capsules returned}) / (\text{total number of capsules planned to be taken})]$. This will be considered as the primary compliance rate.
Compliance based on eDiary data up to week 24	$100 \times (\text{total number of capsules taken up to week 24}) / (\text{total number of capsules planned to be taken up to week 24})$.

VARIABLES	FORMULA
	The number of capsules planned to be taken will be estimated based on patient's body weight per Protocol Table 3. If a patient's weight changes at any time during the study, dose adjustment will be required.
Derivations for Efficacy Parameters	
Baseline (general)	
Baseline 1 is defined as the last value prior to the first dose in Study A4250-005 for patients in Cohort 1.
 
Baseline 2 is defined as the last value prior to the first dose in Study A4250-008 for all patients. For patients in Cohort 1, the pre-dose assessments of Study A4250-008 can be from Study A4250-005.
 
Baseline 2 will be used in all analyses unless otherwise specified.

Baseline for serum bile acids change from baseline	
Baseline 1 is defined for patients in Cohort 1 and will be calculated as the average of last 2 values prior to the first dose in Study A4250-005. If only one non-missing value is available, it will be used as baseline.
 
Baseline 2 is defined as follows:
 
Cohort 1: the average of the last 2 values before the first dose of study drug in Study A4250-008. In general, these 2 values are the values of the last 2 assessments of Study A4250-005. If pre-dose assessments are collected in Study A4250-008 for a patient, then the values of pre-dose assessments in Study A4250-008 will be considered first and used to calculate the baseline. These 2 values need to be taken from 2 consecutive scheduled visits or unscheduled visits. If only one value is available from 2 consecutive scheduled visits or unscheduled visits, then that value will be used as baseline.
 
Cohort 2: the average of last 2 values prior to the first dose in Study A4250-008. If only one non-missing value is available, it will be used as baseline.
 
Baseline 2 will be used in all analyses unless otherwise specified.

End value for serum bile acids change from baseline	The end value is the average of the values at Weeks 70 and 72 after the start of treatment. (Appendix B). If one value is missing, then the non-missing value will be used as the end value. If both values are missing, then the end value is missing.
Baseline, daily, weekly, and monthly score by AM and PM respectively (scratching, itch severity)	
For both the Albireo ObsRO scratching item and the Albireo PRO itch severity score:
 
All non-missing AM scores from the period of 14 days before or on the first dose day of study medications will be averaged as baseline.
 
All non-missing PM scores from the period of 14 days before the first dose day of study medications will be averaged as baseline.
 
Baseline score will be considered missing if ≥ 8 out of 14 assessments in the 14 days are missing (i.e. 50% rule is applied based on the number of planned assessments).
 
A weekly AM (PM) score will be calculated by averaging all non-missing AM (PM) scores in a week. A weekly score will be considered missing if ≥ 4 out of 7 AM (PM) scores in a week are missing.

VARIABLES	FORMULA
	
A monthly AM (PM) score will be calculated by averaging all non-missing AM (PM) scores in a month (28 days). A monthly score will be considered missing if ≥ 15 out of 28 AM (PM) scores a week are missing.
 
An AM (PM) average score at each visit after Week 24 will be calculated by averaging all non-missing AM (PM) scores between 2 visits with analysis windows applied (Appendix B). 50% rule is applied based on the number of planned assessments.

AM & PM baseline, daily, weekly, and monthly score (scratching, itch severity)	
For both the Albireo ObsRO scratching item and the Albireo PRO itch severity score:
 
A daily AM & PM score will be averaged from the 2 ratings for each day. A daily score will be considered missing if both assessments are missing.
 
A weekly score will be calculated by averaging all non-missing AM and PM scores in a week. A weekly score will be considered missing if ≥ 8 out of 14 assessments in a week are missing.
 
A monthly score will be calculated by averaging all non-missing AM and PM scores in a month (28 days). A monthly score will be considered missing if ≥ 29 out of 56 assessments in a month are missing.
 
An average score of AM & PM at each visit after Week 24 will be calculated by averaging all non-missing AM and PM scores between 2 visits with analysis windows applied (Appendix B). 50% rule is applied based on the number of planned assessments.
 
All non-missing AM scores from the period of 14 days before or on the first dose day of study medications, and all non-missing PM scores from the period of 14 days before the first dose day of study medications will be averaged as the AM & PM baseline score. Baseline score will be considered missing if ≥ 15 out of 28 assessments in the 14 days are missing. Rounded baseline score will be used for the analysis.
 
One thing of note:
 
Inclusion criteria No. 4 in Study A4250-005:
 
Cohort 1: Patient must have history of significant pruritus and a caregiver-reported observed scratching in the eDiary average of ≥ 2 (on 0 to 4 scale) in the 2 weeks prior to randomisation in Study A4250-005.
 
Inclusion criteria No. 4 in Study A4250-008:
 
Cohort 2: Patient must have history of significant pruritus and a caregiver-reported observed scratching or patient reported itching (for patients > 18 with no caregiver-reported observed scratching) in the eDiary average of ≥ 2 (on 0 to 4 scale) in the 2 weeks prior to the screening/inclusion visit (Visit 1) in Study A4250-008.
 
The pruritus score for purposes of establishing eligibility was calculated by taking the average of the worse of the two scores for each day. The values for week one were averaged and the values for week 2 were averaged. The two weekly averages were then averaged to provide a single score. If this score was ≥ 2 the pruritus eligibility requirement was met. The calculation of pruritus eligibility score is different from the calculation of the baseline pruritus score defined in the SAP.


VARIABLES	FORMULA
Average of change from baseline from each AM and PM scores (scratching, itch severity)	
The calculation below is based on the change from baseline in each AM and PM score. The values based on this calculation will be used for data analysis.
 
Change from baseline (daily) will be calculated by averaging all non-missing values of change from baseline (AM and PM) in a day. A daily change from baseline will be considered missing if both AM and PM change from baseline in a day are missing.
 
Change from baseline (weekly) will be calculated by averaging all non-missing values of change from baseline (AM and PM) in a week. A weekly change from baseline will be considered missing if ≥ 8 out of 14 change from baseline values in a week are missing.
 
Change from baseline (monthly) will be calculated by averaging all non-missing values of change from baseline (AM and PM) in a month (28 days). A monthly change from baseline will be considered missing if ≥ 29 out of 56 assessments in a month are missing.
 
Change from baseline at each visit after Week 24 will be calculated by averaging all non-missing values of change from baseline (AM and PM) between 2 visits with analysis windows applied (Appendix B). 50% rule is applied based on the number of planned assessments.

Baseline, daily, weekly, and monthly (sleep parameters, such as difficulty falling asleep and staying asleep, tiredness, the number of awakenings)	For patient- and observer-reported outcome scores of sleep parameters, the same approach above will be used as for scratching/itch severity by AM and PM, respectively, since there is just one rating per day.
Proportion of positive pruritus assessments	No imputation will be made for any missing data. The assessments after intercurrent events (premature treatment discontinuation, death, or initiation of rescue treatments such as biliary diversion surgery or liver transplantation) will be treated as missing and excluded from analysis. The proportion of positive pruritus assessments will be calculated based on reported eDiary data only. 50% rule will be applied based on the number of planned assessments (Appendix B).

VARIABLES	FORMULA
Baseline for proportion of responders for pruritus scores	
Baseline 1 is defined as the average of all non-missing daily scores from 14 days prior to the first dose of study drug in study A4250-005.
 
Baseline 2 is defined as the average of all non-missing daily scores from 14 days prior to the first dose of study drug in study A4250-008 (For patients in Cohort 1, the pre-dose assessments of Study A4250-008 can be from Study A4250-005).
 
Baseline score will be considered missing if ≥ 8 out of 14 assessments in the 14 days are missing. The unrounded baseline score will be used for the analysis.

Derivations for Safety Parameters	
AE duration (days)	AE end date–AE start date + 1
TEAEs	An AE (classified by preferred term) occurring during the treatment period and within 28 days follow-up after the last dose that a) has a start date on or after the first dose date of study drug, or b) has a start date before the date of the first dose date of study drug, but worsened in severity on or after the date of the first dose date of study drug. If an AE started in Study A4250-005 and was ongoing at the time of enrolment in Study A4250-008, the AE will not be considered a TEAE unless it worsens in severity on or after the date of the first dose date of study drug.

AE: adverse event; BMI: body mass index; CRF: case report form; eDiary: electronic diary; ObsRO: observer-reported outcome; PFIC: progressive familial intrahepatic cholestasis; PRO: patient-reported outcome; SAP: statistical analysis plan; TEAEs: treatment-emergent adverse events

